16.3 Appendix 3: Specific Renal Alert Criteria and Actions and Event Follow-up

Table 16-4 Specific Renal Alert Criteria and Actions and Event Follow-up

Serum Event	
Serum creatinine increase 25 – 49% compared to baseline	Confirm 25% increase after 24-48h Follow up within 2-5 days
Acute Kidney Injury: Serum creatinine increase \geq 50% compared to baseline	Follow up within 24-48h if possible Consider study treatment interruption Consider patient hospitalization /specialized treatment
Urine Event	
New dipstick proteinuria \geq 3+ OR Protein-creatinine ratio \geq 150 mg/g or \geq 15 mg/mmol	Consider causes and possible interventions 
 • Assess serum albumin & serum total protein • Repeat assessment to confirm • Consider drug interruption or discontinuation unless other causes are diagnosed and corrected
New dipstick hematuria \geq 3+ on urine dipstick	Repeat assessment to confirm 
 • Distinguish hemoglobinuria from hematuria • Urine sediment microscopy • Assess sCr • Exclude infection, trauma, bleeding from the distal urinary tract/bladder, menstruation • Consider bleeding disorder

For all renal events: Document contributing factors in the CRF: co-medication, other co-morbid conditions, and additional diagnostic procedures performed Monitor patient regularly (frequency at investigator’s discretion) until either: Event resolution: sCr within 10% of baseline or protein-creatinine ratio within 50% of baseline, or Event stabilization: sCr level with \pm10% variability over last 6 months or protein-creatinine ratio stabilization at a new level with \pm50% variability over last 6 months.
	

16.4 Appendix 4: Hepatitis B serology results and interpretation

Not Applicable

16.5 Appendix 5: Blood Logs

Table 16-5 (A) - Blood Logs

Period	Visit Name	Days	Weeks		Hematology	Clinical Chemistry	Coagulation Panel ²	Immunology	Cryoglobulins ³	PK blood collection ⁴			Total (mL)
					Size (mL)	Size (mL)	Size (mL)	Size (mL)	Size (mL)	Size (mL)	Sample Number	Dose reference ID	
Extension-Treatment	Wk 60E1 ⁵	421	60		-	-	1.8	-	-	-	-	-	9.3
	Wk 61	428	61		-	-	-	-	-	-	-	-	0
	Wk 62	435	62		-	-	-	-	-	-	-	-	0
	Wk 64	449	64		2	2.5	-	-	-	-	-	-	4.5
	Wk 66	463	66		-	-	-	-	-	-	-	-	0
	Wk 68	477	68		2	2.5	-	6	-	-	-	-	10.5
	Wk 70	491	70		-	-	-	-	-	-	-	-	0
	Wk 72	505	72		2	2.5	1.8	-	2	-	-	-	8.3
	Wk 74	519	74		-	-	-	-	-	-	-	-	0
	Wk 76	533	76		2	2.5	-	6	-	3	101	1	13.5
	Wk 78	547	78		-	-	-	-	-	-	-	-	0
	Wk 80	561	80		2	2.5	-	-	-	-	-	-	4.5
	Wk 82	575	82		-	-	-	-	-	-	-	-	0
	Wk 84	589	84		2	2.5	1.8	6	2	-	-	-	21.8
	Wk 86	603	86		-	-	-	-	-	-	-	-	0
	Wk 88	617	88		2	2.5	-	-	-	-	-	-	4.5

Period	Visit Name	Days	Weeks		Hemato	Clinical	Coagul	Immun	Cryogl	PK blood collection ⁴			Total (mL)
					logy	Chemis	ation	ology	obulins	Size	Sample	Dose	
					logy	try	Panel ²		³		Number	reference ID	
					Size (mL)	Size (mL)	Size (mL)	Size (mL)	Size (mL)	Size (mL)	Size (mL)	Size (mL)	Size (mL)
	Wk 90	631	90		-	-	-	-	-	-	-	-	0
	Wk 92	645	92		2	2.5	-	6	-	3	102	2	13.5
	Wk 94	659	94		-	-	-	-	-	-	-	-	0
	Wk 96	673	96		2	2.5	1.8	-	2	-	-	-	8.3
	Wk 98	687	98		-	-	-	-	-	-	-	-	0
	Wk 100	701	100		2	2.5	-	6	-	-	-	-	10.5
	Wk 102	715	102		-	-	-	-	-	-	-	-	0
	Wk 104	729	104		2	2.5	-	-	-	-	-	-	4.5
	Wk 106	743	106		-	-	-	-	-	-	-	-	0
	Wk 108/ TD ⁶	757	108		2	2.5	1.8	6	2	3	103	3	24.8
Post-Treatment Follow-Up	Wk 112	785	112		2	2.5	-	6	-	-	-	-	10.5
	Wk 120/ EOS ⁷	841	120		2	2.5	-	6	2	3	104	3	15.5
Total 164.5 mL													
¹ [REDACTED] ² While on treatment, coagulation monitoring applies only to participants who have antiphospholipid antibodies (lupus anticoagulant, anti-cardiolipin antibodies) and/or who are on pre-existing antithrombotic therapy/prophylaxis, as reflected in the exclusion criteria of the TWINSS core study protocol. ³ Analysis of cryoglobulins will be done only for participants who were positive at screening in the TWINSS core study. ⁴ Blood sample is collected pre-dose. ⁵ Corresponds to the Week 60 visit of the core study. Assessments carried out as part of Week 60 as per core study protocol can be used for Week 60E1 of the extension study. ⁶ In case of premature discontinuation, participants will enter the follow up after completing assessments for this visit. ⁷ Mandatory to all subjects, including those who have discontinued the study prematurely.													

[figure not shown]
Table 16-6 (B) - Blood Logs

[figure not shown]
Period	Visit Name	Days	Weeks	Immunogenicity ¹		Total (mL)
				Size (mL)	Sample ID	
Extension-Treatment	Wk 60E1 ²	421	60	-	-	0
	Wk 61	428	61	-	-	0
	Wk 62	435	62	-	-	0
	Wk 64	449	64	-	-	0
	Wk 66	463	66	-	-	0
	Wk 68	477	68	-	-	0
	Wk 70	491	70	-	-	0
	Wk 72	505	72	-	-	0
	Wk 74	519	74	-	-	0
	Wk 76	533	76	4	201	6
	Wk 78	547	78	-	-	0
	Wk 80	561	80	-	-	0
	Wk 82	575	82	-	-	0
	Wk 84	589	84	-	-	0
	Wk 86	603	86	-	-	0
	Wk 88	617	88	-	-	0
	Wk 90	631	90	-	-	0
	Wk 92	645	92	4	202	6
	Wk 94	659	94	-	-	0
	Wk 96	673	96	-	-	0
Wk 98	687	98	-	-	0	
Wk 100	701	100	-	-	0	
Wk 102	715	102	-	-	0	

[figure not shown]
Period	Visit Name	Days	Weeks	Immunogenicity ¹		Total (mL)
				Size (mL)	Sample ID	
	Wk 104	729	104	-	-	0
	Wk 106	743	106	-	-	0
	Wk 108/TD ³	757	108	4	203	6
Post-Treatment Follow-Up	Wk 112	785	112	-	-	0
	Wk 120/EOS ⁴	841	120	4	204	6
Total 24.0 mL						

[figure not shown]
¹ Blood sample is collected pre-dose. ² Corresponds to the Week 60 visit of the core study. Assessments carried out as part of Week 60 as per core study protocol can be used for Week 60E1 of the extension study. ³ In case of premature discontinuation, participants will enter the follow up after completing assessments for this visit.

[figure not shown]
⁴ Mandatory to all subjects, including those who have discontinued the study prematurely.

[figure not shown]

[figure not shown]

[figure not shown]

[figure not shown]

[figure not shown]

16.10 Appendix 10: Satisfaction with self-injection using a prefilled syringe questionnaire

Table 16-15 Satisfaction with self-injection using a prefilled syringe questionnaire

Satisfaction with self-injection using a pre-filled syringe
 
INSTRUCTIONS: The following questions ask about your experiences and overall satisfaction with using the pre-filled syringe to give yourself an injection.
 
Please select only one answer for each question.
 
1) How confident do you feel using the pre-filled syringe to give yourself an injection?
 
 Very confident  Quite confident  Moderately confident  A little confident  Not confident at all
 
2) How easy is it to use the pre-filled syringe to give yourself an injection?
 
 Very easy  Quite easy  Moderately easy  A little easy  Not easy at all
 
3) How convenient is it to give yourself an injection to treat your Sjögren's Syndrome?
 
 Very convenient  Quite convenient  Moderately convenient  A little convenient  Not convenient at all
 
4) Overall, how satisfied are you with giving yourself an injection to treat your Sjögren's Syndrome?
 
 Very satisfied  Quite satisfied  Moderately satisfied  A little satisfied  Not satisfied at all
 
5) If you had the option, would you continue to use a treatment that you could self-inject?
 
 Yes, definitely  Yes, probably  I don't know  Probably not  Definitely not

--

16.11 Appendix 11: Study design of core study CCFZ533B2201

Screening	Double-blind treatment Period 1		Double-blind treatment Period 2		Follow-up
6 weeks	24 weeks		24 weeks		12 weeks
	Loading regimen weekly	Maintenance Q2W	Loading regimen weekly	Maintenance Q2W	
	2 weeks (weekly visits)	22 weeks (visits every 2 wks)	2 weeks (weekly visits)	22 weeks (visits every 2 wks)	

The core study will consist of a 6-week screening, 2 treatment periods of 24 weeks each, and a follow-up period of 12 weeks. In Periods 1 and 2, 13 treatment administration visits are planned, including weekly loading regimen (2 visits) at the start of each treatment period. One administration equals two s.c. injections.

Primary analysis will occur at Week 24 including all participants but the analysis for Cohort 1 and analysis for Cohort 2 may occur at different time points depending on patient recruitment and preparation timelines. While maintaining the blinding at Week 24, participants in the placebo arms D and F will be automatically switched to iscalimab (Arms D1 and F1, respectively) for treatment Period 2. All other participants (Arms A, B, C and E) will continue with their randomized iscalimab treatment from Period 1 into Period 2 (additional 24 weeks). The purpose of this second treatment period is to collect longer-term efficacy and safety data in a controlled, double-blinded fashion, while minimizing the number of participants who will continue to receive only placebo.

EULAR FAS IRT LLN LLOQ MedDRA PD PFS	European League Against Rheumatism Full analysis set Full analysis set Interactive Response Technology Interactive Response Technology Iower limit of normal Lower limit of quantification Medical dictionary for regulatory activities Pharmacodynamic(s) Pre-filled syringe
EULAR FAS IRT LLN LLOQ MedDRA PD PFS	European League Against Rheumatism Full analysis set Full analysis set Interactive Response Technology lower limit of normal Lower limit of quantification Medical dictionary for regulatory activities Pharmacodynamic(s) Pre-filled syringe
EULAR FAS IRT LLN LLOQ MedDRA PD PFS	European League Against Rheumatism Full analysis set Interactive Response Technology Iower limit of normal Lower limit of quantification Medical dictionary for regulatory activities Pharmacodynamic(s) Pre-filled syringe
EULAR FAS IRT LLN LLOQ MedDRA PD PFS SAE	European League Against Rheumatism Full analysis set Full analysis set Interactive Response Technology Iower limit of normal Lower limit of quantification Medical dictionary for regulatory activities Pharmacodynamic(s) Pre-filled syringe serious adverse event
EULAR FAS FAS IRT LLN LLOQ MedDRA PD PFS SAE SAE SAF	European League Against Rheumatism Full analysis set Full analysis set Interactive Response Technology Iower limit of normal Lower limit of quantification Medical dictionary for regulatory activities Pharmacodynamic(s) Pre-filled syringe Serious adverse event Safety Set Control of the device Diverse in the set of the
EULAR FAS IRT LLN LLOQ MedDRA PD PFS SAE SAE SAF SAP	European League Against Rheumatism Full analysis set Full analysis set Interactive Response Technology Iower limit of normal Lower limit of quantification Medical dictionary for regulatory activities Pharmacodynamic(s) Pre-filled syringe serious adverse event Safety Set Statistical Analysis Plan
EULAR FAS IRT LLN LLOQ MedDRA PD PFS SAE SAF SAF SAP	European League Against Rheumatism Full analysis set Full analysis set Interactive Response Technology Iower limit of normal Lower limit of quantification Medical dictionary for regulatory activities Pharmacodynamic(s) Pre-filled syringe Serious adverse event Safety Set Statistical Analysis Plan
EULAR FAS FAS IRT LLN LLOQ MedDRA PD PFS SAE SAE SAF SAP SD	European League Against Rheumatism Full analysis set Full analysis set Interactive Response Technology Interactive Response Technology Iower limit of normal Lower limit of quantification Medical dictionary for regulatory activities Pharmacodynamic(s) Pre-filled syringe Serious adverse event Safety Set Statistical Analysis Plan Standard deviation

- SMQStandardized MedDRA QuerySSASjögren's-syndrome-related antigen A
- TBL Total Bilirubin
- TEAE Treatment emergent adverse events
- ULN upper limit of normal
- VAS Visual analog scale

1 Introduction

The purpose of this Statistical Analysis Plan (SAP) is to describe the implementation of the statistical analysis planned in section 12 of the study protocol.

This document covers the statistical and analytical plans for the analysis of all data collected up to the end of the study.

1.1 Study design

Study CCFZ533B2201E1 (TWINSS extension) is a continuation of the core study CCFZ533B2201 and is planned as a multicenter trial. This study will offer continuation of treatment for participants who have completed the core study and are deemed by the Investigator to clinically benefit from continued iscalimab therapy. The primary purpose of this 1-year extension study is to provide additional safety and tolerability information of the two doses of iscalimab (iscalimab 600 mg and 300 mg) administered via prefilled syringes (PFS).

A total of 206 participants from both Cohort 1 and Cohort 2 of the core study were enrolled. Study blinding for the extension study will be maintained until final database lock of the core study, upon which the participants and Investigators will be unblinded, making it an open-label study through Week 120 (end of study visit). All visit numbers (in weeks) used in the extension study are relative to the baseline visit of the core study CCFZ533B2201. The baseline visit for the extension study (Week 60E1) will be carried out on the same day as the Week 60 visit of the core study.

The extension study is a 48-week treatment study, with a safety follow-up period of 12 weeks (Figure 1-1). Participants who complete 48 weeks of treatment and the mandatory 12 weeks of follow-up in the core study CCFZ533B2201 are eligible to participate in the extension study. The 12 weeks of follow-up in the core study is considered mandatory to obtain PK data. The extension study will help to evaluate the sustainability of response (ESSDAI) after a year of treatment in the core study.

Upon completion of treatment Period 2 (Week 48) of the core study, Investigators will use their clinical judgment to decide if it is beneficial for participants to continue with the extension study based upon response to therapy at the end of the treatment period. All participants will be considered for participation in the extension study. A new Informed Consent must be signed before proceeding into the extension study. The participant should provide their informed consent prior to the start of the Week 60 assessments of the core study.

The treatment will be administered via pre-filled syringe (PFS) in the extension study. This is a change from the core study, which used s.c. injections prepared from vials. During the treatment period, 25 treatment administration visits are planned, including a weekly loading regimen. All participants enrolled in the extension study will receive a weekly loading regimen (Week 60E1, Week 61, Week 62) at the start of the treatment period followed by a s.c. maintenance regimen (600 or 300 mg s.c. every 2 weeks (Q2W)). One administration equals two s.c. injections.

To maintain extension study blinding until final database lock of the core study, an Interactive Response Technology (IRT) algorithm will be used to re-assign participants to either iscalimab

600 mg (Arm 1) or 300 mg (Arm 2) s.c. Q2W in the extension study using ESSDAI (Cohort 1 of core study) or ESSDAI and ESSPRI (Cohort 2 of core study) scores at predefined time points (Weeks 4 (or Week 0 in case of a missed visit) and 48 (or Week 40 in the case of a missed visit)) in the TWINSS core study.

Participants will be instructed in detail how to self-administer the s.c. injection using the PFS formulation. Each injection will be administered into an appropriate injection site of the body (thighs, arms, or abdomen). For the first four visits of the study (through Week 64), all injections will be performed at the study site. If a participant had good safety and tolerability, with no indication of hypersensitivity or other acute reactions from the previous doses, starting from Week 66, the participant is allowed to self-administer the study treatment at home according to the assessment schedule. The participant may continue to present at 2 week intervals to the study site for injection administrations, based on the participant's preference and the Investigator's judgment. Site staff will administer the injection to participants who are not able or unwilling to self-administer the PFS injection. The treatment period is from Week 60E1 to Week 108.

Figure 1-1 Study design

RASGN - new treatment reassignment; s.c. - subcutaneous

Treatr	Treatment period					
4	8 weeks	12 weeks				
Loading regimen weekly	Maintenance Q2W					
2 weeks (weekly visits)	46 weeks every 2 wks (alternating monthly site visits with home administrations)					

1.2 Study objectives and endpoints

The objectives and related endpoints planned in the Clinical Study Report (CSR) are listed in Table 1-1.

Table 1-1 Objectives and related endpoints

Objective(s)	E	Endpoint(s)				
Primary objective(s)	E	Endpoint(s) for primary objective(s)				
• To evaluate the safety and iscalimab at two dose level 300 mg) in patients with Sj participated in the TWINSS CCFZ533B2201	tolerability of s (600 mg and S, who S core study,	Incidence of Treatment-emergent adverse events (TEAEs)/ serious adverse events (SAEs) Routine hematology and clinical chemistry laboratory test results at analysis visits up to end of study Vital signs at analysis visits up to end of study				
Secondary objective(s)	E	ndpoint(s) for secondary objective(s)				
 To assess the pharmacokin levels) and dose-exposure iscalimab 	netics (PK trough • relationship of	Free iscalimab concentration in plasma during the treatment (Ctrough) and follow- up (up to end of study) periods				
• To assess immunogenicity	of iscalimab •	Incidence of anti-iscalimab antibodies in plasma at analysis visits up to end of study				

2 Statistical methods

2.1 Data analysis general information

Novartis will perform the analyses for this study. Statistical software SAS version 9.4 or later will be used.

Summary statistics for continuous variables will include N, mean, standard deviation, minimum, lower quartile, median, upper quartile, maximum. Summary statistics for discrete variables will be presented in contingency tables and will include absolute and relative frequencies.

If not otherwise specified, two-sided confidence intervals will be displayed. Unless otherwise stated, the level of significance will be set to 5% (two-sided).

All safety listings will be presented by treatment sequence from extension study.

All efficacy/PRO listing will be presented by core study cohort and extension treatment group

Only descriptive statistics will be provided, no inferential statistics will be conducted.

2.1.1 General definitions

2.1.1.1 Study treatment

CFZ533 (iscalimab) 600 mg or 300 mg will be administered s.c., weekly for the first 3 doses (Weeks 60E1, 61 and 62); then, from Week 64, iscalimab will be administered s.c. bi-weekly (every other week or Q2W). This is illustrated in Figure 2-1 for Arm 1 (iscalimab 600 mg maintenance regimen) and Arm 2 (iscalimab 300 mg maintenance regimen).

- For participants assigned to the iscalimab 600 mg maintenance regimen (Arm 1), the loading doses are 600 mg on Week 60E1, 61 and 62, followed by a bi-weekly maintenance regimen at 600 mg.
- For participants assigned to the iscalimab 300 mg maintenance regimen (Arm 2), the loading doses are 600 mg on Week 60E1, and 300 mg on Week 61 and Week 62, followed by a bi-weekly maintenance regimen at 300 mg.

Figure 2-1 Iscalimab doses and regimen

^a 600 mg s.c.: 2 injections of 2 mL iscalimab (300 mg/2 mL); ^b 300 mg s.c.: 1 injection of 2 mL iscalimab (300 mg/2 mL) and 1 injection of 2 mL placebo; ^c every other week (bi-weekly) s.c. administration

2.1.1.2 Study Day 1 and other study days

The first day of administration of study treatment in extension study is defined as Study Day 1 or Day 1.

All other study days will be labeled relative to Day 1. For event dates on or after Day 1, study day for a particular event date is calculated as [Date of event] – [Date of first dose]+1, i.e., Day 2, Day 3, etc., will be one day, two days, etc., after Day 1, respectively. For the dates before Day 1, study day for an event date is calculated as [Date of event] – [Date of first dose], i.e., Day -1, Day -2, etc., will be one day, two days, etc., before Day 1, respectively. Duration of an event will be calculated as (Event end date – Event start date + 1).

The descriptor "Day 0" will not be used.

2.1.1.3 Baseline and post-baseline definitions

Baseline (Week 60E1) is defined as the last assessment (including unscheduled visits) obtained before the first dose of study treatment in extension study. All assessments obtained after first dose of study treatment at extension study are considered as post-baseline unless otherwise specified.

2.1.1.4 Day of last dose of study treatment

The dates will be derived based on data collected on the Dose Administration Record (DAR) page of the eCRF. The subject's exposure will be calculated considering the last dosing visit plus 14 days.

2.1.1.5 Last day of study period

The last date of study period will be collected via the CRF. The subject's study period will be calculated considering the end of study period visit (e.g., study completion visit).

2.1.1.6 Visit window

Visit-windows will be used for the summary by visit, which are based on the study evaluation schedule and comprise a set of days around the nominal visit day. For any assessment, there are protocol defined scheduled visits around which visit windows were created to cover the complete range of days within the study. The visit windows are shown in Table 2-1. In this table, the days are counted since the first dose of study treatment (study days) for both efficacy and safety assessments in the extension study. These visit windows apply to measurements taken at every visit. For assessments collected less often, different visit windows will be applied as detailed below.

When visit windows are used, all visits will be re-aligned, i.e., they will be mapped into one of the visit windows. E.g., if the *Week 62* visit of a subject is delayed and occurs on Day 449 (Day 29 relative to the first dose date of the extension study) instead of on Day 435 (Day 15 relative to the first dose date of the extension study), it will be re-aligned to visit window *Week 64*. In the case of major deviations from the visit schedule, or due to unscheduled visits, several assessments of a subject may fall in a particular visit window (either scheduled or unscheduled). Statistical approaches to handle multiple assessments in a given visit window are specified below.

516	Table	5 2-1	· · ·	133033	ment	windo	WS IOI SCHOU	uicu	VISILS	in the	CALCINS	ion stut	a y
Study Period	Analysis	lysis get	Analysis Windows										
	VISIC	Day		Grou p2		Group 4		Grou p7	Grou p 8				
	Week 60E1 (Baselin e)	1		<= 1*		<= 1*		<= 1*	<= 1*				
	Week 61	8		2 - 11		14							
	Week 62	15		12 – 22									
Extens ion	Week 64	29		23 - 43		2 - 43							
	Week 66	43						с х					
	Week 68	57		44 – 71		44 – 71							
	Week 70	71											
	Week 72	85		72 - 99		72 - 99			2 – 127				

Table 2-1	Assessment windows for scheduled visits in the extension study
-----------	--

Novartis
SAP Amendment 3

2	3		 		 	
	Week 74	99				
	Week 76	113	100 - 127	100 – 127		
	Week 78	127				
	Week 80	141	128 - 155	128 - 155		
	Week 82	155				
	Week 84	169	156 - 183	156 - 183		128- 211
	Week 86	183				1912-192
	Week 88	197	184 - 211	184 - 211		
	Week 90	211				
	Week 92	225	212 - 239	212 - 239		
	Week 94	239				
	Week 96	253	240 - 267	240 - 267		212- 295
	Week 98	267				
	Week 100	281	268 - 295	268 - 295		
	Week 102	295				
	Week 104	309	296 - 323	296 - 323		
	Week 106	323				
	Week 108	337	324 - EoP3	324 – EoP3	2 – EoP 3	296 – EoP3
Post- Treatm ent	Week 112	365	(EoP3 +1)- 393	(EoP3 +1) - 393		
Follow -Up	Week 120	421	394- EoS	394- EoS		(EoP3 +1) - EoS

* The first dose date of the extension study is defined as Day 1.

Group 2: Vital signs,

Group 4: Hematology, Clinical Chemistry, Urinalysis Dipstick pregnancy, Physical Examinations, SSSD
Group 7: ECG
Group 8: Cryoglobulins, Hepatitis and CMV monitoring
Group 11: Immunology

The visit window will not be used for the listings.

Full Analysis Set (FAS): The FAS comprises all participants to whom study treatment for the extension study has been assigned by the re-assignment algorithm. For analysis on FAS, participants will be analyzed according to the treatment group to which they have been assigned. Only data in the extension study will be included in the analysis.

Summaries of extension data in FAS will be based on the core study cohort assignment and reassigned treatment groups.

- Cohort 1 CFZ533 600 mg
- Cohort 1- CFZ533 300 mg
- Cohort 2 CFZ533 600 mg
- Cohort 2 CFZ533 300 mg

Safety Set (SAF): The Safety Set includes all subjects who received at least one dose of study treatment. Subjects will be analyzed according to the actual treatment received. The safety set will be used in the analysis of all safety variables.

The actual treatment received in a period is defined as the treatment dose level (including loading dose) that a subject was most frequently exposed to during the period. The frequency will be calculated using data collected on the Dose Administration Record (DAR). In case a subject is exposed to more than one dose level for the same number of times during a period, the actual treatment is the earliest one administered to the subject in that period.

Summaries of extension data in SAF will be based on the re-assigned treatment groups.

- CFZ533 600 mg
- CFZ533 300 mg

The PK Set (PKS) includes all subjects who received at least one dose of iscalimab treatment and have quantifiable PK measurements of iscalimab. Analysis of plasma PK, will be based on PKS and by the iscalimab treatment dose level a subject is most frequently exposed to, including the loading dose, during the study. Only data in the extension study will be included in the analysis.

Summaries of extension data in PKS will be based on the re-assigned treatment groups.

- CFZ533 600 mg
- CFZ533 300 mg

The IM Set (IMS) includes all subjects who received at least one dose of iscalimab treatment and have quantifiable immunogenicity measurements of iscalimab. Analysis of immunogenicity data will be based on PKS and by the iscalimab treatment dose level a subject is most frequently exposed to, including the loading dose, during the study. Only data in the extension study will be included in the analysis.

Summaries of extension data in IMS will be based on the re-assigned treatment groups.

- CFZ533 600 mg
- CFZ533 300 mg

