12.1 Analysis sets

The Full Analysis Set (FAS) comprises all participants to whom study treatment for the extension study has been assigned by the re-assignment algorithm. For analysis on FAS, participants will be analyzed according to the treatment group to which they have been assigned. Only data in the extension study will be included in the analysis.

The Safety Set (SAF) includes all participants who received at least one dose of study treatment during the extension study. Participants will be analyzed according to the study treatment received, where treatment received is defined as the assigned treatment if the participant took at least one dose of that treatment or the first treatment received if the assigned treatment was never received. Only data in the extension study will be included in the analysis.

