2.3 Treatments (study treatment, rescue medication, concomitant therapies, compliance)

2.3.1 Study treatment / compliance

The analysis of study treatment data will be based on the safety set.

Duration of exposure will be defined as the time from first dose of study medication to the last dose date plus 14 days.

For subjects who completed treatment, there is a visit window of \pm 5 days for the 14 days. For subjects who discontinued treatment, the EoT disposition date is the last assessment date in treatment period. Therefore, the EoT visit was not considered ideal for the end of exposure calculation and the current exposure calculation method is proposed:

Duration of exposure (days) = (last dose date + 14 days) - first dose date +1

Duration of exposure (weeks) = duration of exposure (days) / 7

The number and percentage of patients in SAF who are exposed to study treatment for prespecified time intervals (every two weeks) will be summarized for the overall study. Patients who receive any wrong study medications will be listed.

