2.7 Interim analysis

There is no interim analysis planned for the study.

3 Change to protocol specified analyses

- New broader definition of TEAE than defined in the protocol

4 Appendix

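### Under the SAP's most-frequent-dose rule, a correctly dosed 300 mg participant who stops after one or two doses is analysed as 600 mg; the two-dose case conflicts with protocol 12.1 and is not declared.

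*SAP*

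**What the plan says.** **The SAP rule.** In the SAP's Analysis sets text (after Section 2.1.1.7), the Safety Set is analysed by actual treatment. This is "the treatment dose level (including loading dose) that a subject was most frequently exposed to during the period", counted from the dose administration record. If two levels are equally frequent, "the actual treatment is the earliest one administered to the subject in that period".

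**A second grouping sentence.** The same paragraphs add: "Summaries of extension data in SAF will be based on the re-assigned treatment groups". The SAP does not say whether this overrides the rule or only names the two columns.

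**The schedule.** For the 300 mg arm (Arm 2), SAP 2.1.1.1 states that "the loading doses are 600 mg on Week 60E1, and 300 mg on Week 61 and Week 62", followed by 300 mg every two weeks. Protocol 4.2 gives the same sequence. Arm 1 receives 600 mg throughout.

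**The protocol rule.** In protocol 12.1, "treatment received is defined as the assigned treatment if the participant took at least one dose of that treatment". The first treatment received is used only if the assigned one was never received.

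**Declared changes.** SAP Section 3 lists one item: "New broader definition of TEAE than defined in the protocol".

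**PK and immunogenicity sets.** Both are grouped "by the iscalimab treatment dose level a subject is most frequently exposed to, including the loading dose, during the study". No tie rule is given for either.

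**The concern.** The rule looks designed to catch misdosing, but it also moves people who were dosed correctly. Arm 2's first scheduled dose is at the other arm's level, so a short, fully compliant Arm 2 record looks like a 600 mg record. The movement goes one way, from 300 mg to 600 mg.

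The people who move are not a random subset. They stopped treatment very early, and protocol 9.1.1 makes stopping mandatory for some adverse events, including serious or severe infections. If the rule governs, their treatment-emergent events and their exposure are reported under 600 mg. The Safety Set carries the primary safety tables (protocol 12.4, SAP 2.4) and the exposure analysis (SAP 2.3.1). An early safety problem in the 300 mg arm would then be credited to the higher dose, under a rule that departs from the protocol without saying so.

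**Working it through.** **1. Reproduce the number of doses.** Weeks 60E1, 61 and 62 give 3. Weeks 64 to 106 every two weeks give (106 - 64)/2 + 1 = 22. The total is 25, which matches the 25 administration visits stated in protocol 3 and SAP 1.1. The sequences are therefore Arm 2 = 600, then 24 x 300; Arm 1 = 25 x 600.

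**2. Apply both rules to Arm 2, cut after each number of doses.** Protocol 12.1 is run twice because it does not say whether treatment means a dose level or the assigned regimen.

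| Doses taken | 600 mg : 300 mg | SAP rule | Protocol 12.1, dose level | Protocol 12.1, assigned regimen |
|---|---|---|---|---|
| 1 | 1 : 0 | 600 | 600 | 300 |
| 2 | 1 : 1 (tie, earliest) | **600** | **300** | **300** |
| 3 | 1 : 2 | 300 | 300 | 300 |
| 25 | 1 : 24 | 300 | 300 | 300 |

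From 3 to 25 doses every column gives 300 mg. Arm 1 dosed as scheduled is 600 mg at every number of doses. So the SAP and the protocol conflict at two doses on either reading, and at one dose only on the regimen reading.

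**3. Who is affected.** Protocol 6.5.2 permits no interruption until Week 66 is completed. On-schedule participants with one or two doses are therefore permanent stoppers before the Week 62 dose.

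**4. What moves with them.** SAP 2.4 counts treatment-emergent events to the last dose plus 98 days, or study end if earlier. With nominal dose days 1 and 8:
- One dose: 1 + 98 = Day 99.
- Two doses: 8 + 98 = Day 106.

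The exposure formula is "Duration of exposure (days) = (last dose date + 14 days) - first dose date +1":
- One dose: (1 + 14) - 1 + 1 = 15 days.
- Two doses: (8 + 14) - 1 + 1 = 22 days.

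**5. PK and immunogenicity sets.** A one-dose Arm 2 stopper is 600 mg. A two-dose stopper is tied 1-1 with no tie rule, so has no defined group. The case can arise: the blood logs in protocol 16.5 schedule samples at the treatment-discontinuation and end-of-study visits, and early stoppers attend both.

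**6. Size, by illustration.** The documents give 206 enrolled (SAP 1.1) but no arm sizes and no count of early stoppers. The splits, event counts and number moved (m) below are assumptions. The event is uncommon, for example an adverse event leading to discontinuation, and everyone who moves is assumed to have had it. The rates are (e300 - m)/(n300 - m) and (e600 + m)/(n600 + m).

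| Split 300/600 | m | 300 mg | 600 mg | 600 minus 300 |
|---|---|---|---|---|
| 103/103 | 0 | 5/103 = 4.9% | 5/103 = 4.9% | 0.0 |
| 103/103 | 1 | 4/102 = 3.9% | 6/104 = 5.8% | 1.8 |
| 103/103 | 2 | 3/101 = 3.0% | 7/105 = 6.7% | 3.7 |
| 70/136 | 0 | 3/70 = 4.3% | 6/136 = 4.4% | 0.1 |
| 70/136 | 1 | 2/69 = 2.9% | 7/137 = 5.1% | 2.2 |
| 136/70 | 0 | 6/136 = 4.4% | 3/70 = 4.3% | -0.1 |
| 136/70 | 1 | 5/135 = 3.7% | 4/71 = 5.6% | 1.9 |

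Gaps are in percentage points, from unrounded rates. One such participant shifts the gap by about 2 points in each split. If those who move (one or two) did not have the event, the shift is 0.2 points or less. If nobody moves, it is zero.

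**The case against.** **The re-assigned groups may govern.** If that sentence decides the grouping, nobody moves and nothing conflicts with protocol 12.1. This is a possible reading, and it is why the point is stated conditionally. But the most-frequent rule and its tie rule would then do nothing, and the statement that participants are analysed by actual treatment would be wrong. On either reading the text needs correcting.

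**The loading-dose parenthesis may mean that the 600 mg dose counts as part of the 300 mg regimen.** That would remove the problem. The SAP does not say it, and a count of dose levels with a tie rule for exposure to more than one level points to counting each dose at its own level.

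**The effect is small and partly visible elsewhere.** This stands. The analysis is descriptive, the arms are not randomised, all adverse events are listed, and the Full Analysis Set disposition table (SAP 2.2.1) shows premature study discontinuations by assigned arm. The 2-point figure also supposes that everyone who moves had the event.

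**Stronger readings that the documents do not support.**
- A reader might infer that the rule changes who is in the Safety Set. It does not: one dose is enough for entry, and only the treatment group changes.
- A reader might infer that the one-dose case contradicts the protocol outright. If treatment means dose level, that participant never received 300 mg, and 12.1 also gives 600 mg.
- A reader might infer that an exposure table would show every 300 mg participant at four weeks or more, because three doses give 29 days at nominal dates. SAP 2.3.1 plans the interval counts for the study overall, and protocol 12.3 does not clearly promise them by arm. Within the visit windows of protocol 8, three doses can also give as few as 26 days (26/7 = 3.7 weeks).

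**Conclusion.** The concern holds as a minor, conditional point. If the most-frequent-dose rule decides the Safety Set grouping, a 300 mg participant dosed as scheduled who stops after one or two doses is analysed as 600 mg. The two-dose case contradicts protocol 12.1 on any reading; the one-dose case does so only on the regimen reading. SAP Section 3 declares neither. Independently of that condition, the SAP's two Safety Set grouping sentences have to be reconciled, and the PK and immunogenicity sets leave a two-dose Arm 2 stopper without a defined group.

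The classification follows from the stated schedule and rules and needs no assumption beyond counting doses by level. The size is not known: it depends on how many participants stopped this early, which is probably few and may be none. No inferential result depends on it. The point concerns analysis grouping only and says nothing about the dosing schedule itself.

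**What to change.** Replace the most-frequent-dose and tie rules with the protocol 12.1 rule, and state that treatment means the assigned regimen including its scheduled loading doses. A participant dosed as scheduled then stays in the assigned arm at every number of doses. Apply this to the Safety, PK and immunogenicity sets, make the sentences on re-assigned groups consistent with it, and list every participant whose analysed group differs from the assigned arm.

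There is one trade-off. On this reading an Arm 2 participant given 600 mg at every visit stays in 300 mg, because the first dose belongs to the assigned regimen. The listing of wrong study medication already planned in SAP 2.3.1 would show such a case. If the sponsor wants the grouping itself to detect sustained misdosing, it could match each administration to the two regimen schedules and send ties to the assigned arm. On-schedule participants stay put under that rule too. Arm 2 given 600 mg at all 25 visits becomes 600 mg (25 matches to 1), and Arm 1 given 300 mg at all 25 becomes 300 mg (24 to 0). That rule departs from 12.1 in some cases: an Arm 1 participant given 600 mg, then 300 mg in error, who stops would be 300 mg (2 matches to 1). It must therefore be declared in Section 3.

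The cost is one paragraph of SAP text, one derivation in the subject-level dataset and one short listing, plus a line in Section 3 if a different rule is kept. No new data are needed.
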